To minimize risk relating to questionnaire and interview assessments: It is possible that some children and adolescents and parents may become slightly anxious or upset when asked to attend to their anxious thoughts or feelings as required by these procedures. We anticipate such reactions will be short-lived in nature and typically have no significant long-term consequences. In fact, many children and parents are likely to benefit from an improved self-understanding derived from the completion of these measures. These measures are standard and widely used in this age range, and there have been no reports of negative iatrogenic effects. Participants and their parents are not required to answer questions during interviews or on questionnaires that they find too sensitive.

To minimize risk relating to blood draw: Venipuncture will be performed by qualified and experienced personnel in an approved location at the Yale University Department of Laboratory Medicine. Trained, qualified and experienced personnel reduce the risk of pain, bleeding, redness, inflammation, ecchymosis, phlebitis and infection. Qualified locations reduce risks that accompany fainting. The amount of blood to be drawn, not more than 15ml, is well within what is permissible and should not present risk. Participants will be able to decline to have the blood draw at any time until it is completed.

To minimize risk relating to behavioral interactions: Parent and child will each be able to terminate the entire interaction, or part of it at any time. Children and parents will be given instructions that they may stop whenever they want. The graduate research associates also have been carefully and thoroughly trained in the providing of reassurance. Similar procedures have been widely used for many years without report of negative results. In addition, the research associate will spend some time with the participants following each assessment procedure and discuss the participants' reactions to the procedure.

To minimize risk relating to treatment: Changes in parents' behavior (e.g., reducing their accommodation of the child's anxiety) involves some risk of children feeling upset, becoming angry, or parents' experiencing anxiety. Every treatment session includes a review of the past week and query for any uncomfortable events. Any description of extreme exacerbation in parent or child anxiety; suicidal or self-injurious behavior; or other potentially harmful or dangerous event will be reviewed clinically and addressed. The therapists will report any such event immediately to the PI. Co-investigator [name] has many years of experience working with anxious children and their parents, including in multiple large scale clinical trials and will oversee the project closely. Upon consultation, a determination will be made about the most appropriate manner in which to intervene (e.g., alternative treatment, hospitalization, etc.), and the child or parent will be excluded from the study, as necessary.

To minimize risk relating to cognitive and behavioral tasks: Participants can stop the tasks at any time and are reminded of this prior to beginning them.

To minimize risk relating to MRI: All FDA guidelines for MRI scanning are carefully observed at the Yale MRRC and Yale BIC. All of the scans will be performed using an MRI scanner employing pulse sequences and hardware that have been approved by the FDA. The field strength is 3 Tesla and all relevant operating characteristics (RF power deposition, rate of change of the field gradients, coil design) fall within the limits of FDA guidelines.

Participants will be carefully screened to exclude those who may have metal in or on their bodies that cannot be removed. We conduct a thorough metal screening at both the phone screening and again at the beginning of the MRI visit to ensure that the participant's status is still safe for MRI scanning. Yale MRRC and Yale BIC rules strictly forbid staff from entering the magnet room carrying metal objects.

Because the MRI procedure requires participants to lie still in a tunnel-like device for a considerable length of time, some participants can find the confinement or noise uncomfortable. We provide ear protection to soften the noise level for participants. We also use an extensive simulation procedure at the mock MRI scanner during the first visit to help participants acclimate to the MRI environment. Especially for children and adolescents, this is helpful to get used to the feeling of staying still in the tunnel and hearing the types of sounds that the scanner makes. Participants who experience claustrophobia during the mock MRI scan or who endorse claustrophobia on the screening will not be scheduled for the MRI scan. Based on our prior publications that have used this procedure, we are confident that the mock scan will be helpful for acclimating to the MRI environment (e.g., [name] et al., 2012; [name] et al., 2013a; [name] et al., 2013b; [name] et al., 2014; [name] et al., 2016). All participants are given a button to signal distress so that they can stop the scan at any time. Participants also use an intercom to communicate with the experimenter during the scan.

At all times, participants will have the option to discontinue the scan if they find it to be objectionable in any way. We can allow them to take additional breaks, if desired, in between image sets, but if that is not acceptable, they are free to discontinue at any time. Participants will be paid for their participation in the MRI visit regardless, without any worry of bias because of their level of participation.

In accordance with Yale MRRC policy, the MRI scan is for research purposes only. As specified in the consent form, participants are explicitly told that the scans are not designed to find abnormalities. If a worrisome finding is seen on a scan, a radiologist or other physician will be asked to review the relevant images. Based on his/her recommendation (if any), the PI or consulting physician will contact the participant, inform the participant of the finding, and recommend that the participant seek medical advice as a precautionary measure. However, the decision for additional examination or treatment would lie only with the participant and their physician.

There is minimal risk involved in the collection of physiological data. Participants can choose not to participate at any time if they experience discomfort (e.g., stickiness) from the adhesive and can remove the adhesive and wash the skin off at any time.

In the opinion of the PI, scheduling MRI scans on days the child is not taking stimulant medication will not increase risks.

Consent and Assent documents will review all relevant risks and protections, including risk to confidentiality, as detailed in the appropriate sections below.

12. Data and Safety Monitoring Plan: Include an appropriate Data and Safety Monitoring Plan (DSMP) based on the investigator's risk assessment stated below. (Note: the HIC will make the final determination of the risk to subjects.)

- a. What is the investigator's assessment of the overall risk level for subjects participating in this study? Minimal risk.
- b. If children are involved, what is the investigator's assessment of the overall risk level for the children participating in this study? Minimal risk.
- c. Include an appropriate Data and Safety Monitoring Plan. Examples of DSMPs are available here <http://your.yale.edu/policies-procedures/forms/420-fr-01-data-and-safety-monitoring-plans-templates> for
 - i. Minimal risk
 - ii. Greater than minimal

The data and safety monitoring plan for this study will follow the guidelines developed by the Yale University Biomedical Institutional Review Board and are based on the requirements of the NIH and the NIMH guidance on Risk-Based Monitoring (<https://www.nimh.nih.gov/funding/clinical-research/nimh-guidance-on-risk-based-monitoring.shtml>). The plan provides a description of the procedure for monitoring and evaluating the progress of the intervention trial, and the mechanism for reporting adverse events.

Drs. [name]. (PI), [name]. (Co-I), [name]. (Co-I), and [name] M.D. (Co-I) will monitor the safety of study participants to ensure that they do not incur undue risk. The safety monitoring will focus on clinical functioning of the participants as well as the assessment and intervention procedures including fMRI assessments. Drs. [name], [name], [name] and [name] will also continually reassess risks versus benefits throughout the study period.

The level of risk for this study is low. In general, no serious adverse risks are seen associated with either the assessment, intervention, or MRI procedures. The assessment procedures are widely used, and non-invasive and parent-based treatment has been used in many clinical trials and has not been found to carry any significant risk. SPACE is a novel intervention but has been piloted in multiple clinical trials and has not been found to carry any significant risk.

[name] has decades of experience conducting clinical trials for childhood anxiety disorders, including of parent-based interventions. [name] has implemented SPACE with many families directly and supervised other clinicians in this approach and has served as PI of a randomized clinical trial of SPACE. During the project, as part of the safety monitoring procedures, PI [name] and Co-I [name] will conduct weekly supervision meetings with therapists for purposes of monitoring child clinical

functioning. This will include reviewing therapist notes etc. for monitoring participant safety. [name] has decades of experience studying brain response using fMRI in children and adults. [name] has experience using fMRI to study brain response and anxiety including in young children and serves as PI on another study utilizing fMRI to study brain response and anxiety in childhood. The study team including Drs. [name], [name], [name], and [name] will meet weekly to discuss study progress including any concerns that arise.

As in any therapeutic endeavor it is possible that some children could react adversely during the assessment and/or intervention procedures. All adverse events will be carefully monitored by the Co-PIs. The occurrence of any serious unexpected adverse event (e.g., threats to one's life and/or others, suicidal attempts, etc.) will be reported by the Co-PIs to the university IRB within 5 days. The Co-PIs, Yale University IRB, Yale Magnetic Resonance Research Center (MRRC), Yale Brain Imaging Center (BIC), and Yale Pediatric Protocol Review Committee (PPRC) have the authority to stop or suspend the study or require modifications. The Co-PIs and Co-Is will also make biannual reviews of safety and adverse events.

Confidentiality: All subject information will be de-identified and stored separately with only a subject identification number. The key to the ID numbers will be stored electronically on a secure encrypted computer accessible only with a password by the Co-PIs, Co-Is and IRB.

- d. For multi-site studies for which the Yale PI serves as the lead investigator: N/A
 - i. How will adverse events and unanticipated problems involving risks to subjects or others be reported, reviewed and managed? Write here
 - ii. What provisions are in place for management of interim results? Write here
 - iii. What will the multi-site process be for protocol modifications? Write here

13. Statistical Considerations: Describe the statistical analyses that support the study design. General Overview. Data management protocols will be used to ensure data integrity. Missing values (including fMRI data) will be estimated using chained equation multiple imputation algorithms.¹⁰⁸ Analyses will focus on least squares test (OLS) of means and modern robust estimation procedures⁹⁴ that rely on Wilcox's R routines (which generally have more statistical power than traditional OLS)⁹⁵. If non-normality or outliers appear problematic, we will use the Wilcox functions base on M estimation. We will examine associations between arm and baseline variables to ensure successful randomization. Our analytic approach follows NIH guidelines on rigor and reproducibility, including analysis of sex as a potential covariate. Aim 1: Demonstrate target engagement. Child reliance on parent for amygdala reactivity reduction (calculated as the difference between amygdala reactivity to fear faces in the parent-absent compared to parent-present scan, and from hereon referred to as 'child reliance on parent') will decrease significantly from PRE to POST treatment for children whose parents participate in SPACE, as compared with children whose parents participate in CBT. The assessments of interest for this question are PRE and POST. The additional time-point (MID) will be useful to gain preliminary insights relating to more complex questions of mediation. The OLS analysis is a

2-group single degree of freedom contrast between SPACE and CBT using child reliance on parent at PRE as a covariate to increase statistical power. The single degree of freedom contrast focuses on the comparison of covariate-adjusted means at POST. Of interest is whether the contrast between arms is statistically significant for child reliance on parent; the direction of change will be determined by the sign of the parameter estimates. A dummy variable for the two arms (SPACE, CBT) will be included in the OLS analysis, with randomization to SPACE scored 1 and randomization to CBT scored 0. A statistically significant negative parameter estimate of the effect of treatment arm on child reliance on parent indicates that reduction in child reliance on parent at POST is significantly greater following SPACE compared with CBT. The same analysis will be conducted for mPFC activation and for amygdala-mPFC functional connectivity.

SECTION II: RESEARCH INVOLVING DRUGS, BIOLOGICS, RADIOTRACERS, PLACEBOS AND DEVICES

If this section (or one of its parts, A or B) is not applicable, check off N/A and delete the rest of the section.

A. RADIOTRACERS ☒ N/A

B. DRUGS/BIOLOGICS ☒ N/A

B. DEVICES ☒ N/A

SECTION III: RECRUITMENT/CONSENT AND ASSENT PROCEDURES

1. Targeted Enrollment: Give the number of subjects:

- a. Targeted for enrollment at Yale for this protocol: 226 children and their mothers, for a total of 452 participants
- b. If this is a multi-site study, give the total number of subjects targeted across all sites:

Write here:

2. Indicate recruitment methods below. Attach copies of any recruitment materials that will be used.

- ☒ Flyers ☒ Internet/web postings ☐ Radio ☐ Tabling
☐ Posters ☐ Mass email solicitation ☐ Telephone
☒ Letter (postcard) ☒ Departmental/Center website ☐ Television
☐ X Blog posting with approved messaging/advertising
☐ Newsletter via email
☐ X messaging/advertising on music-listening platforms
☐ Medical record review* ☒ Departmental/Center research boards ☐ Newspaper
☒ Departmental/Center newsletters ☒ Web-based clinical trial registries ☒
 Clinicaltrials.gov
☒ YCCI Recruitment database
☒ Other: The Yale Child Study Center Anxiety & Mood Disorders Program sees children with anxiety disorders and those who meet study criteria will be offered the opportunity to

participate in the study. ☒ Social Media (Twitter/Facebook):

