**HRP-503B – BIOMEDICAL RESEARCH
PROTOCOL (2017-1)**

Protocol Title: Brain response associated with parent-based treatment for childhood anxiety disorders

Principal Investigator: [name]

Version Date: Click or tap here to enter text.

(If applicable) **Clinicaltrials.gov Registration #:** NCT03585010

INSTRUCTIONS

This template is intended to help investigators prepare a protocol that includes all of the necessary information needed by the IRB to determine whether a study meets approval criteria. **Read the following instructions before proceeding:**

1. Use this protocol template for a PI initiated study that includes direct interactions with research subjects. Additional templates for other types of research protocols are available in the system Library.
2. If a section or question does not apply to your research study, type “Not Applicable” underneath.

SECTION I:

1. Statement of Purpose:

Anxiety disorders impact up to one-third of children, cause tremendous suffering, increase risk for psychiatric and medical morbidity, impair school and social functioning, and cost billions of dollars each year. Data consistently show that child anxiety is characterized by amygdala hyperactivity and deficits in prefrontal control of the amygdala. Emerging data link these disruptions to anxious children's over-reliance on parents for amygdala- medial prefrontal cortex (mPFC) engagement and anxiety reduction. This study aims to test whether an entirely parent-based psychosocial treatment with no child involvement, Supportive Parenting for Anxious Childhood Emotions (SPACE), engages an amygdala-mPFC target in anxious children, lessening child reliance on parents to reduce amygdala reactivity.

Offspring's natural reliance on parents for anxiety reduction is magnified in clinically anxious children. Parents become deeply enmeshed in their child's symptoms through the process of family accommodation, defined as change in parents' behavior to help the child avoid or alleviate anxiety. In clinically anxious children, 90% report depending on parents to reduce their anxiety, and 97% of parents report accommodating their anxious child's symptoms. Anxious children's reliance on parents for anxiety reduction may disrupt the child's ability to independently reduce amygdala reactivity and anxiety.

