The study will examine clinically anxious children's amygdala-mPFC response to fear faces when (A) the child's parent is beside them holding their hand during the fMRI scan (Parent-Present), and (B) the child is alone during the scan (Parent-Absent) (within-subjects design). Children with primary anxiety disorder diagnoses will serve as participants. Children will complete Parent-Present and Parent-Absent scans PRE- and POST-SPACE, or PRE- and POST-CBT (Cognitive-behavioral therapy), an established treatment of equal duration and therapist-parent contact.

Aim 1: Demonstrate SPACE lessens children's reliance on parents to reduce amygdala reactivity (i.e., target engagement).

Aim 2: Demonstrate associations between target engagement and anxiety outcomes.

Aim 3: Establish feasibility and acceptability of SPACE, as well as patient satisfaction.

2. Probable Duration of Project: 5 years.

3. Background: Describe the background information that led to the plan for this project.

Provide references to support the expectation of obtaining useful scientific data.

Anxiety disorders comprise the most prevalent disorders of childhood and adolescence. If not treated successfully, anxiety disorders cause significant short and long-term impairment and pose huge financial and societal costs (Costello, Egger, & Angold, 2005) through factors such as increased school dropout, teenage childbearing, and lost productivity in the workplace (Compton et al., 2004; Greenberg et al., 1999). Despite strong evidence for the efficacy of cognitive-behavior therapy (CBT), up to 50% of children remain symptomatic after treatment

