The study is a clinical trial involving children with primary anxiety disorders. Children will randomly be assigned to one of two treatment conditions.. One condition is Supportive Parenting for Anxious Childhood Emotions (SPACE) which focuses on reducing family accommodation of child anxiety symptoms. The comparator condition is cognitive-behavioral therapy (CBT) an established and evidence-based treatment for childhood anxiety disorders, of known efficacy. In CBT children will be introduced to and discuss the presenting problem, review treatment rationale and goals, work with the therapist to devise an anxiety hierarchy, and participate in in-session and out-of-session exposure tasks. Additionally, children will be introduced to the cognitive component of treatment by identifying faulty cognitions and generating incompatible self-statements, and exploring alternatives. . Families will be randomly assigned to one of the aforementioned conditions. After initial screening, children will first participate in a pre-treatment assessment (PRE). The PRE assessment will include: a structured interview with child and parent covering anxiety symptoms and related conditions, questionnaires completed by child and parent, a brief parent-child interaction which is video-taped, collection of blood and saliva (see procedures below). Following the PRE assessment, eligible patients will be randomized into either SPACE or CBT and will undergo a neuroimaging scan using fMRI to examine behavioral and brain processes associated with anxiety and fear processing.

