In the SPACE treatment condition parents participate in 12 weekly parent-only sessions. In the CBT treatment condition children participate in 12 weekly child-only sessions. Parents of children assigned to CBT will meet with the child's therapist three times over the course of the treatment study, to be kept informed about their child's progress and provide helpful information to the therapist. Sessions can take place in person at the Yale Child Study Center or over secure video-link using the HIPAA approved Zoom software provided by Yale University. Participants will choose whether to have the sessions in person or over zoom and can elect to have some in person and some over Zoom. Youth and parents will be re-assessed after 6 treatment sessions (MID) and after the 12th session (POST). These assessments include the same procedures done at the first assessment, except the MID assessment does not include clinical interviews. After the 12th treatment session children will also undergo a second neuroimaging scan using fMRI. In both treatment conditions participants will be invited back for a follow-up visit 6-months from their initial appointment. At this appointment, these assessment procedures are the same as the MID assessment, but does not include a video-taped interaction or saliva sample.

Participants who are already enrolled will be invited to electronically complete an optional set of questionnaires related to their experiences during the COVID-19 pandemic (Please see Measures for list of questionnaires). This part of the study is completely optional. The questionnaires will be administered via the HIPAA-secure REDCap platform. Participants will receive \$15 when they submit the completed questionnaires.

Assessment Procedures:

Each of these three assessments (PRE, MID, POST) will be conducted in single sessions at our clinic by carefully trained independent evaluators (IE). Each assessment session will include collection of biological samples, behavioral observation, and self-report measures. During the youth interview, the parent will be administered the questionnaires and vice versa.

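### The Statement of Purpose says CBT matches SPACE on parents' contact with the therapist, but the Research Plan schedules 12 parent sessions in SPACE and 3 parent meetings in CBT

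*Combined protocol and SAP*

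**What the plan says.** The Statement of Purpose (Section I, item 1) describes CBT as "an established treatment of equal duration and therapist-parent contact". That asserts two equalities with SPACE: length of treatment, and contact between therapist and parent.

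The Research Plan (Section I, item 4) sets the schedule:

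- For SPACE: "In the SPACE treatment condition parents participate in 12 weekly parent-only sessions".
- For CBT: "In the CBT treatment condition children participate in 12 weekly child-only sessions".
- Also for CBT: "Parents of children assigned to CBT will meet with the child's therapist three times over the course of the treatment study". The stated purpose of these meetings is "to be kept informed about their child's progress and provide helpful information to the therapist".

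Other parts of the protocol agree with this schedule on who is treated. The Statement of Purpose itself calls SPACE "an entirely parent-based psychosocial treatment with no child involvement". The Research Plan describes the content of CBT as work with the child ("In CBT children will be introduced to and discuss the presenting problem"). Recruitment Procedures (Section III, item 3) labels the SPACE arm as parent-only and the CBT arm as child-only.

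**The concern.** The two descriptions of the comparator cannot both be right. One says parents see the therapist equally often in both arms. The other gives SPACE parents a weekly session and CBT parents three meetings in total.

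The mismatch bears on interpretation. SPACE is meant to work through parents, by reducing their accommodation of the child's anxiety, and the Aim 1 outcome is how far the child relies on the parent to reduce amygdala reactivity. If parent contact really were equal, a SPACE-CBT difference could not be put down to SPACE parents simply having had more contact with a therapist. With unequal contact, that explanation stays open. A reader who took the Statement of Purpose at its word, or a report that repeated it, would treat the explanation as closed by design.

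**Working it through.** The plan gives no numerical figure to reproduce. Its claim is verbal and amounts to a parent-contact ratio of 1:1. The check is a count of scheduled contacts.

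**Inputs**, all from the Research Plan (Section I, item 4) except the last:

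- SPACE sessions with parents: 12, weekly.
- CBT sessions with the child alone: 12, weekly.
- CBT meetings between parents and therapist: 3 over the whole treatment.
- SPACE sessions with the child: 0 (Statement of Purpose, Section I, item 1).

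**Counts by arm**

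| Scheduled contact | SPACE | CBT | Equal? |
|---|---|---|---|
| Weekly treatment sessions | 12 | 12 | Yes |
| Parent with therapist | 12 | 3 | No |
| Child with therapist (treatment sessions) | 0 | 12 | No |
| All contacts, parent meetings additional | 12 | 12 + 3 = 15 | No |
| All contacts, parent meetings within existing visits | 12 | 12 | Yes |

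**Parent contact**

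- Ratio: 12 / 3 = 4.
- Difference: 12 − 3 = 9 fewer in CBT.
- CBT as a share of SPACE: 3 / 12 = 25%.

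**Can any reading restore equality of parent contact?**

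1. *Counting the CBT treatment sessions as parent contact.* The Research Plan specifies that these are for the child only, so they cannot be counted.
2. *Longer CBT parent meetings.* With SPACE sessions of length s and CBT parent meetings of length m, equal time needs 3m = 12s, so m = 4s. Session lengths are not given for either arm, and nothing suggests that CBT parent meetings last four times as long as a SPACE session.
3. *The phrase is a slip for total therapist contact.* The last two rows of the table apply: 12 against 15, or 12 against 12. The protocol does not say whether the three parent meetings are extra visits. Even on this reading the clause needs correcting, because it names parent contact.

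The equal-duration half of the claim holds in the sense that both arms have 12 weekly sessions. The parent-contact half does not hold under any reading of the schedule.

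**The case against.** The strongest reply is that nothing in the analysis uses the disputed clause. The Aim 1 text in Statistical Considerations (Section I, item 13) compares covariate-adjusted means between arms coded by randomisation. It never invokes contact matching, and it makes no claim about the content of SPACE net of parent contact. The true schedule is also disclosed in the same protocol, and the arms are labelled consistently elsewhere. One descriptive clause is out of step with an otherwise coherent design. All of this stands, and it is why the severity is low. It does not make the clause true, and the Statement of Purpose is a summary that may be carried into reports.

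A second reply is that total therapist contact may have been meant, in which case the arms are equal or close to it. The documents neither confirm nor exclude this, so the fix allows for it.

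A reader might also fault the Aim 1 hypothesis for comparing outcomes "for children whose parents participate in SPACE, as compared with children whose parents participate in CBT", as if parents took part equally in both arms. The documents do not support that criticism. CBT parents do take part, through three meetings; the phrase says nothing about amount; and the model description that follows defines the contrast by randomised arm. That text needs no rewording.

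**Conclusion.** Wrong as written; low severity. The Statement of Purpose gives the comparator a property that the schedule does not provide. Scheduled parent contacts are 12 in SPACE and 3 in CBT (4:1, a difference of 9), while weekly treatment sessions are 12 in each arm. A SPACE-CBT difference is one between a parent-based and a child-based package and should not be described as controlled for amount of parent contact.

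The conclusion rests on counting scheduled contacts and on reading the clause as it stands, as parent contact. Session lengths are not given, so no ratio of contact time is claimed.

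Two stronger readings are tempting and unsupported:

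- *That unequal parent contact biases or invalidates the Aim 1 comparison.* It does not. The arms are randomised as packages, unequal parent contact follows naturally from comparing a parent-based with a child-based treatment, and the planned test answers that question.
- *That the number of parent meetings would itself drive the outcome.* No part of the protocol links the amygdala measure to the number of meetings. The point is only that this explanation has not been excluded by design.

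**What to change.** In the Statement of Purpose (Section I, item 1), reword the one clause. It should say that CBT is matched to SPACE on duration and number of weekly treatment sessions (12 each) but not on therapist-parent contact (12 sessions in SPACE, 3 meetings in CBT). It should add that a SPACE-CBT difference is therefore between a parent-based and a child-based package and is not controlled for amount of parent contact.

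The sponsor should confirm the intended meaning first. If total therapist contact was meant, the clause should say so and state whether the three CBT parent meetings are additional (12 against 15) or fall within existing visits (12 against 12).

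The cost is wording in one place. The only drawback is a less favourable description of the comparator. The treatment schedule, sample, data collection, the Aim 1 text and the model stay as they are.
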